5.8.3 Additional Adverse Events for Review

Summaries of Additional TEAEs for review will be summarized by SOC and PT. All SMQs based on MedDRA Version 17.1 are listed below and will include broad and narrow terms.

Additional AEs for review are:

- Drug-induced hepatotoxicities (cholestasis and jaundice of hepatic origin SMQ, hepatic failure, fibrosis, cirrhosis, and other liver damage-related conditions SMQ, hepatitis, noninfectious SMQ, liver neoplasms, benign [including cysts and polyps] SMQ, liver malignant tumors SMQ, liver tumors of unspecified malignancy SMQ, liver-related investigations, signs and symptoms SMQ, liver-related coagulation and bleeding disturbances SMQ)
- Cardiac events (cardiomyopathy SMQ, cardiac failure SMQ, and arrhythmia related investigations, sign and symptoms SMQ)
- Thrombocytopenia (hematopoietic thrombocytopenia SMQ)
- Port-related events (embolic and thrombotic events, venous SMQ, extravasation events (injections, infusions, and implants) SMQ, PTs in the following High Level Terms (HLT): sepsis, bacteremia, viremia and fungemia NEC (not elsewhere

classified), implant and catheter site reactions, PTs in the following HLGs: endocardial disorders, and device issues. In addition, a search will be performed on the verbatim terms for “port”, “central venous” and “central line”). Note: The port-related events will only be identified for patients who have a port placed/inserted and for events that occur after the port insertion occurred. It is noted that port insertion may occur during treatment or prior to the start of treatment. Percentages will be calculated based on the total number of patients who have had a port inserted

A corresponding listing will be generated for each table. Additionally, a table and listing corresponding to the additional AEs for review that were related to study drug or moderate or severe will be produced.

An overall summary of additional AEs for review will include total number of events, number of serious events, number of related events, number of not related events, number of mild events, number of moderate events, number of severe events, and number of events occurring on the same day as an infusion.

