12.2. Definition of Adverse Events

12.2.1. Adverse Event (AE)

An AE is any untoward medical occurrence in a clinical trial participant, which does not necessarily have a causal relationship with the investigational drug. An AE can, therefore, be any unfavorable and unintended symptom, sign, disease, condition, or test abnormality that occurs during or after administration of an IP whether or not considered related to the IP. AEs include:

- Symptoms described by the patient or signs observed by the Investigator or medical staff.
- Test abnormalities (laboratory tests, ECG, X-rays, etc) that result in an alteration in medical care (diagnostic or therapeutic).

Abnormalities present at baseline are considered AEs only if they reoccur after resolution or worsen during the AE collection period.

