12.4. Recording Adverse Events

All AEs/SAEs experienced from the time of informed consent to the last follow-up will be recorded within each patient's CRF. Information should include: a concise description of the event; date and time of event onset and resolution; determination of seriousness, severity, corrective treatment, outcome, and relationship to IP or study procedure or underlying disease; and any action taken will be recorded. Resolution occurs when the patient has returned to his baseline state of health or further improvement or worsening of the event is not expected.

Whenever possible, a diagnosis will be recorded as an AE, rather than symptoms or isolated laboratory abnormalities related to that diagnosis. Several symptoms or laboratory results that are related to the same diagnosis can thus be part of the same AE. A medical or surgical procedure is not an AE; rather the condition leading to the procedure should be recorded as the AE. Similarly, death is not an AE, but is rather the outcome of the AE(s) that resulted in death. If the AE(s) leading to death are not known, then death must be reported as an AE. All AEs will be followed until the resolution of AE, completion of the patient's study participation, or study termination, whichever occurs first. SAEs will be followed until resolution or until the condition stabilizes or returns to baseline status.

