5.8.1 Adverse Events

In general, only TEAEs will be summarized (for untreated subjects, AEs that first occur or worsen in severity after the study enrollment are considered treatment-emergent). Non-treatment-emergent adverse events will be recorded in the data listings. Unless noted otherwise, for all AE tables, the number and percentage of patients reporting AEs will be grouped using the MedDRA, SOC, and PT and summarized for treated patients, untreated patients, and overall.

An overall summary table of adverse events will be produced and will include the frequency count and percentage of patients with

- TEAE
- Treatment-related TEAE
- Severe TEAE
- Treatment-Emergent SAE
- Treatment-Emergent Related SAE
- TEAE leading to discontinuation of study drug
- TEAE leading to death

The number of events at each severity level (mild, moderate, severe) will also be included.

Multiple occurrences of the same AE (at the PT level) in the same patient will be counted only once in frequency tables. If a patient experiences multiple episodes of the same event with a different relationship/severity, the event with the strongest relationship or maximum severity to investigational drug product will be used to summarize AEs by relationship and severity.

The following summary tables will be produced:

- TEAEs by SOC and PT
- TEAEs by SOC, PT and severity
- TEAE by PT in descending frequency
- Treatment-related TEAEs by SOC and PT
- Treatment-related TEAEs by SOC, PT, and severity
- Treatment-related TEAEs by PT in descending frequency
- Treatment-Emergent SAEs by SOC and PT
- Treatment-related Treatment-Emergent SAEs by SOC and PT
- TEAEs leading to treatment discontinuation by SOC and PT
- TEAEs leading to death by SOC and PT
- Non-serious TEAEs by SOC and PT, displaying both number of subjects and number of events

The following listings will be produced:

- All AEs
- AEs leading to treatment discontinuation
- SAEs

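### The SAP's cardiac event search lists no query for diagnosed arrhythmias or conduction disorders, so such diagnoses may be missed from the Section 5.8.3 cardiac outputs

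*SAP*

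**What the plan says.** SAP Section 5.8.3 sets out groups of additional adverse events for review, each retrieved by standard MedDRA queries (SMQs). The cardiac group is "Cardiac events (cardiomyopathy SMQ, cardiac failure SMQ, and arrhythmia related investigations, sign and symptoms SMQ". On scope, the section says "All SMQs based on MedDRA Version 17.1 are listed below and will include broad and narrow terms". The term lists themselves are not reproduced.

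The hepatic group in the same section uses eight queries. Most are named for conditions, such as non-infectious hepatitis, hepatic failure and cholestasis, and they stand beside "liver-related investigations, signs and symptoms SMQ". The port-related group also has a free-text supplement, introduced by "In addition, a search will be performed on the verbatim terms for". The cardiac group has none.

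Each group feeds a SOC/PT table with a listing, a further table and listing for events that were drug-related or moderate or severe, and an overall summary of event counts by seriousness, relatedness, severity and coincidence with an infusion day.

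Protocol Section 12.4 gives the recording rule: "Whenever possible, a diagnosis will be recorded as an AE, rather than symptoms or isolated laboratory abnormalities related to that diagnosis". Protocol Section 12.2.1 includes among adverse events "Test abnormalities (laboratory tests, ECG, X-rays, etc) that result in an alteration in medical care (diagnostic or therapeutic".

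**The concern.** Within the cardiac group, cardiomyopathy and cardiac failure each have a query named for the condition. Arrhythmia has only a query named for investigations, signs and symptoms. The recording rule in the protocol pulls the other way: once symptoms lead to a diagnosis, the site is asked to enter the diagnosis. An event that is well worked up may then carry a preferred term that no listed query is named for, while an unexplained palpitation is the kind of term the arrhythmia query is named for.

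Section 5.8.3 exists to give one pooled view of cardiac events. If diagnosed arrhythmias are not retrieved, that view is incomplete, and a reader could take an empty or short cardiac table as evidence that no arrhythmia occurred. Safety is the primary objective of the trial, and the protocol's background section describes the disease as involving cardiac muscle.

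**Working it through.** The plan states no figure on this point, so the check compares texts, followed by one line of arithmetic for scale.

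**1. Which kind of query covers which condition (SAP 5.8.3)**

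| Condition | Query named for the condition | Query named for tests, signs and symptoms |
|---|---|---|
| Cardiomyopathy | yes | none listed |
| Cardiac failure | yes | none listed |
| Arrhythmia and conduction disorders | none listed | yes |
| Liver | several | yes |

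Arrhythmia is the only row without a condition-named query.

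**2. How an event would be recorded (Protocol 12.2.1 and 12.4)**

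- *Palpitations, no diagnosis reached.* Recorded as a symptom. This is the kind of term the listed arrhythmia query is named for.
- *An ECG abnormality that changes care, no diagnosis reached.* An adverse event under 12.2.1. Again the kind of term the query is named for.
- *Palpitations followed by a diagnosed arrhythmia.* Under 12.4 the diagnosis is entered where possible, and the symptoms can form part of that same event. No listed query is named for this term.

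The gap therefore concerns the third case. The rule in 12.4 speaks of symptoms and laboratory abnormalities. It does not say that ECG findings are to be absorbed into a diagnosis.

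**3. Does running the queries broad close the gap?** Broad scope widens what each listed query retrieves, but it does not add a query. Whether any arrhythmia diagnosis enters through the arrhythmia, cardiomyopathy or cardiac failure query depends on the MedDRA 17.1 term lists, which the documents do not contain. The point stays open on the documents.

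**4. Other places where the event could appear**

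- *General AE outputs (SAP 5.8.1).* These include "TEAEs by SOC and PT", with tables by severity, relatedness and seriousness and a listing of all AEs. A diagnosed treatment-emergent arrhythmia would be there whatever its SMQ membership.
- *ECG tables (SAP 5.8.6, Appendix Table 5).* ECGs on treatment are scheduled at Weeks 24, 48, 72 and 96. The table has criteria for QTcF, QRS conduction and PR. It has no rhythm criterion, and its markedly-abnormal entry for heart rate is NA.
- *Vital signs (SAP 5.8.5, Appendix Table 4).* These are measured at weekly infusions, and pulse below 60 or above 130 is flagged. This screens rate, not rhythm.

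These outputs limit the consequence, but none of them feeds the 5.8.3 cardiac group.

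**5. Scale**

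- Planned treated group: n of about 20 (SAP 3.3). The denominator is the treatment-group total (SAP 4.1).
- Change in the cardiac-event percentage for each boy missed, if he has no other retrieved cardiac event: 100 × 1/20 = 5 percentage points.
- If he has another retrieved cardiac event, the patient percentage is unchanged. Only the event counts and the seriousness, relatedness and severity breakdowns could be short.
- Expected loss: not computable, because the documents give no arrhythmia rate and no term list.

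**The case against.** The strongest reply is that retrieval is decided by term lists, not by query names. All the queries are run with broad and narrow terms, so the documents cannot show that a single arrhythmia diagnosis is missed. That stands, and it is why the point is that such diagnoses may be missed. A reader might infer that diagnosed arrhythmias do fall outside the table and that the cardiac counts are biased low. The documents do not establish either. Underestimation needs both an arrhythmia and a confirmed failure to retrieve it.

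Second, Protocol 12.4 applies only where possible and refers to laboratory abnormalities, while 12.2.1 keeps care-altering ECG abnormalities reportable. This also stands. It narrows the mechanism to symptoms that are replaced by a diagnosis, but does not remove it.

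Third, the events remain visible elsewhere. Every treatment-emergent event is tabulated and listed, the AE incidence endpoint is unaffected, cardiac events are not among the adverse events of special interest, and the safety analyses are descriptive. All correct: the possible loss is confined to the 5.8.3 cardiac outputs. It would also go too far to call AE reporting the main route by which an arrhythmia would be seen, given weekly pulse measurements and centrally read ECGs.

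Fourth, the SAP states no rule that every group must pair a condition query with a tests-and-symptoms query. Hypersensitivity, renal toxicity and thrombocytopenia each rely on a single SMQ. So the hepatic list suggests an omission but does not prove one. Those single queries are, however, each named for the condition itself. Arrhythmia is the one condition represented only by its tests, signs and symptoms, and the SAP gives no reason.

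**Conclusion.** The concern holds in a limited form. The stated cardiac search names no arrhythmia or conduction diagnosis, and the protocol's recording rule steers sites towards such diagnoses. If the plan is followed as written, a diagnosed arrhythmia may be missing from the 5.8.3 cardiac table, its drug-related or moderate-to-severe subset, its summary counts and its listing. The general AE tables, the all-AE listing and the AE incidence endpoint are not affected.

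The conclusion assumes that the query names reflect their content, which the documents do not let one check. The 5 points per boy assume the planned group of about 20 and that the missed event is his only cardiac event. A comparison of a 0% table with some higher true percentage would need an arrhythmia rate, and none is given. The point is worth correcting because the change is specific and cheap, not because a loss has been shown.

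**What to change.** In SAP Section 5.8.3, add to the cardiac group a query covering arrhythmia and conduction disorders as diagnoses, and keep the existing investigations, signs and symptoms query beside it. Then review the preferred-term list that the combined search produces, confirm that arrhythmia and conduction diagnoses are retrieved, and attach or reference the list. If the review shows that the queries already listed retrieve them, the SAP should say so.

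The cost is one line of SAP text, a longer term list and a short check of that list. No new data are needed. The only downside is that a few more events may appear in one descriptive table.

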5.8.4 Clinical Laboratory Evaluation

Clinical chemistry, hematology, coagulation, and urinalysis results will descriptively be summarized by treatment group and by selected time point. Baseline value, highest/lowest postbaseline value, and final observation and the corresponding change from Baseline will be summarized for treated patients and untreated patients. Frequency tables of patients with potentially clinically significant laboratory parameter values at any time point will be generated. The total number of potentially clinically significant values will also be summarized. Potentially clinically significant values can be found in Appendix 1 tables 1-3.

A shift table will present the number and percentage of patients in each cell resulting from cross-tabulating the status (low, normal, and high) of the highest/lowest postbaseline value versus that of the baseline for each laboratory test, if applicable, by treatment group. If a specific test can have both a significant low and high, then a shift table will be generated for each direction. The percentage will be based on the total number of patients in the Safety Set.

All patient-level clinical laboratory values will be displayed in data listings. In addition, values meeting the potentially clinically significant abnormalities criteria will be presented in data listings. Treatment-emergent abnormalities will be indicated in the listing.

5.8.5 Vital Signs and Other Physical Findings

Vital signs, height/length, and weight will be summarized by treatment group and by selected time point. Baseline value, highest/lowest postbaseline value, and final observation and the corresponding change from Baseline will be summarized for treated patients, untreated patients. Highest/lowest value is considered as the largest absolute change from Baseline for systolic blood pressure, diastolic blood pressure, and respiratory rate, and highest value for pulse rate and temperature. The highest/lowest value will not be summarized for height, weight, or ulnar length. Frequency tables of patients with potentially clinically significant vital sign values will be generated. The

total number of potentially clinically significant values will also be summarized. Potentially clinically significant values can be found in Appendix 1 Table 4.

Vital signs will be listed for all patients. In addition, values meeting the predefined markedly abnormal criteria will be presented in a data listing. Treatment-emergent abnormalities will be indicated. Height and weight will also be listed.

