14.8.2.4. Electrocardiograms

The actual value and change from Baseline to each visit will be presented by visit, summarizing the actual values and change from Baseline to each visit for each parameter using descriptive

statistics. Shift and frequency tables of predefined change abnormal of select ECG parameter values will be generated.

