4. GENERAL STATISTICAL METHODS AND CONVENTIONS

4.1. General Methods

Summary statistics will be presented by treatment group, unless stated otherwise. Treatment group refers to patients receiving eteplirsen and patients in the untreated group.

For continuous variables, descriptive statistics will include the number of patients with data to be summarized (n), mean, standard deviation, median, minimum, and maximum.

For categorical/qualitative variables, descriptive statistics will include frequency counts and percentages. The total number of patients in a treatment group will be used as the denominator for percentage calculations, unless stated otherwise.

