5.8.6 Electrocardiograms and Echocardiograms

For each ECG parameter, the Baseline value, the highest/lowest postbaseline value, final observation, and the corresponding change from Baseline will be summarized for treated patients and untreated patients. The highest/lowest ECG value is the largest change for QT Interval corrected by the Fridericia Correction Formula (QTcF), QRS and PR intervals, highest value for QT, and largest absolute change for heart rate. Frequency tables of patients with potentially clinically significant ECG values will also be generated. The total number of potentially clinically significant values will also be summarized. Potentially clinically significant values can be found in Appendix 1 Table 5.

For each ECHO parameter, including the left ventricular ejection fraction (LVEF) value, Baseline value, final observation, and the corresponding change from Baseline will be summarized for treated patients and untreated patients. Frequency tables of predefined markedly abnormal ECHO values will also be generated. Markedly abnormal values can be found in Appendix I Table 5.

All patient-level values for ECG and ECHO variables will be displayed in a data listing. In addition, values meeting the predefined markedly abnormal criteria will be presented in a data listing. Treatment-emergent abnormalities will be indicated.

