6. CHANGES IN PLANNED ANALYSES

6.1. Changes from Clinical Protocol-Planned Analyses

Compared to protocol specified analyses, the changes are made as follows:

- CCI [REDACTED]
- CCI [REDACTED]
- The observed values and changes from baseline for clinical laboratory assessments, vital signs and ECG will only be summarized for baseline, the last visit (final observation) and the highest/lowest values. All clinical laboratory assessments, vital signs and ECG results by visit will be in data listing.
- The untreated patient group is intended to evaluate the natural history of the DMD disease for patients who are not amenable to exon 51 skipping and is not considered eligible as a current control group for eteplirsen treated patients due to the following: 1) only 7 patients not amenable to exon 51 skipping were enrolled as supposed to planned 20 patients in untreated group, 2) untreated patients have much less assessment frequency of adverse events during study, 3) most untreated patients have dropped out the study earlier. Thus, no direct comparison is made between eteplirsen treated patients and untreated patients. No hypothesis test, no p-value and no inferential statistics will be made for comparison of eteplirsen treated patients and untreated patients.
- Due to complexity of identifying an external control dataset, the statistical methods for the identification and use of the external control dataset will not be described in this SAP. No analysis of eteplirsen-treated patients as compared to an external control will be performed.
- If an external control is identified in the future, the analysis results may not be included in the CSR, and may be reported in a standalone report.
- CCI [REDACTED].
- No other changes are planned or made.

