Appendix Table 4. Vital Sign Abnormalities of Interest

Variable	Units	Markedly Abnormal Criteria Lower limit	Markedly Abnormal Criteria Upper limit
Systolic blood pressure	mmHg	<90	>140
Diastolic blood pressure	mmHg	<40	>90
Pulse rate	beats/minute	<60	>130
Respiratory rate	breaths/min	<12	>20
Temperature	°C	<36.0	>38.0
Weight	kg	Decrease of 7% or more	NA

NA = not applicable

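### The largest-absolute-change summary for systolic BP, diastolic BP, respiratory rate and ECG heart rate merges rises and falls; two signed rows (maximum and minimum change) would read more clearly

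*SAP*

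**What the plan says.** SAP 5.8.5 sets out the continuous display for vital signs: "Baseline value, highest/lowest postbaseline value, and final observation and the corresponding change from Baseline will be summarized". It then defines the middle item: "Highest/lowest value is considered as the largest absolute change from Baseline for systolic blood pressure, diastolic blood pressure, and respiratory rate". Pulse rate and temperature follow a different rule (highest value) and are not part of this point. SAP 5.8.6 uses the same device for one ECG variable: "largest absolute change for heart rate".

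The protocol (14.8.2.2 and 14.8.2.4) planned change from Baseline at every visit. SAP 6.1 withdraws that: laboratory, vital-sign and ECG results "will only be summarized for baseline, the last visit (final observation) and the highest/lowest values", with by-visit results left to listings. SAP 4.1 fixes the statistics: "descriptive statistics will include the number of patients with data to be summarized (n), mean, standard deviation, median, minimum, and maximum". The SAP does not say whether the change shown for the selected reading keeps its sign.

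Other planned outputs bear on direction. SAP Appendix 1, Table 4 gives lower and upper limits for systolic BP (<90, >140), diastolic BP (<40, >90), respiratory rate (<12, >20) and pulse rate (<60, >130), and patients and values beyond these limits are counted and listed. Appendix Table 5 gives ECG heart rate normal limits of 60 and 130 but marks its markedly abnormal criterion as not applicable.

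**The concern.** A rule based on the largest absolute change picks whichever extreme lies further from Baseline. One child is represented by a fall and the next by a rise, and both enter the same mean and median. A child whose readings reached +18 and −17 contributes +18 only. If ten children are selected at +20 and ten at −20, the signed row has mean 0 and SD 20.5, although every child moved by 20.

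Safety is the primary objective and its analysis is descriptive, so these displays are the result. Anything between Baseline and the last visit reaches a change summary only through this row. Treated children have vital signs taken before and at several times after each infusion, so the row condenses several hundred readings per child into one number of mixed direction. No planned row shows how large the typical child's largest fall was, or the typical child's largest rise.

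**Working it through.** The plan has no figure to reproduce: there is no sample-size calculation and no assumed SD.

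**Inputs from the documents**
- Treated vital-sign readings (Protocol 2, footnote d): 4 per weekly infusion over 96 weeks, less the pre-first-dose reading that serves as Baseline, plus one at End of Study: 96 × 4 − 1 + 1 = 384. If reduced to 2 per infusion after 52 weeks: 52 × 4 + 44 × 2 − 1 + 1 = 296.
- Treated ECGs after Baseline: Weeks 24, 48, 72 and 96, so 4.
- Treated group: about 20 children.

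**Assumptions (not in the documents)**
- Within-child SD of one reading, s: 6, 8 or 10 mmHg for BP; 2, 3 or 4/min for respiratory rate; 8, 10 or 12 bpm for ECG heart rate.
- Readings are independent and normal, with a stable mean and a single-reading Baseline of the same SD.

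**Definitions.** For each child, c_j = reading j − Baseline, M = max c_j, m = min c_j. The planned value is P = M if M > |m|, otherwise m. The discarded value is the other one.

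**No effect, BP (groups of 20)**

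| s | 95% range of mean of P (296; 384 readings) | 95% range of median of P (296; 384) | Mean size kept / discarded (296) |
|---|---|---|---|
| 6 | −9.7 to 9.9; −10.1 to 10.0 | −20.6 to 20.7; −21.1 to 21.0 | 22.2 / 12.3 |
| 8 | −12.9 to 13.2; −13.5 to 13.1 | −27.3 to 27.6; −28.2 to 28.1 | 29.6 / 16.4 |
| 10 | −16.8 to 15.9; −16.7 to 16.5 | −34.4 to 34.3; −35.3 to 35.1 | 37.1 / 20.4 |

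Ratio discarded to kept: 12.3/22.2, 16.4/29.6 and 20.4/37.1 are each about 0.55. Hand check at s = 8: P has SD about 30, and 1.96 × 30/√20 ≈ 13.

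Split into two rows at s = 8 (384 readings), M averages about +24 and m about −24, each with SD about 8.5. A 20-child mean of either row then varies by about 1.96 × 8.5/√20 ≈ 3.7 around its own centre.

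Respiratory rate, no effect: the mean of P ranges over about ±3.3, ±5.0 and ±6.7/min.

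**Does splitting detect an effect better?** Signal-to-noise = |mean with effect − mean without| ÷ (SD/√20).

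| Scenario | Planned row P | One-direction row | Sum M + m |
|---|---|---|---|
| Two readings 20 mmHg lower per child, s = 6 / 8 / 10 | about 2.1 / 0.8 / 0.4 | 3.6–3.8 / 1.7–1.9 / 0.8–0.9 | about 2.2 / 0.9 / 0.4 |
| Two readings 8/min higher per child, s = 2 / 3 / 4 | 3.1–3.5 / 1.0–1.2 / 0.4–0.5 | 5.6–6.0 / 1.9–2.2 / 0.8–0.9 | 3.3–3.5 / 1.1–1.2 / 0.4–0.5 |
| ECG heart rate +5 bpm, s = 8 / 10 / 12 | 2.37 / 1.85 / 1.54 | 2.30 / 1.82 / 1.54 | – |

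The one-direction column cannot be used in practice, because it subtracts a no-effect mean that nobody reading the report will have. With no effect, the mean of m is about −17, −23 and −29 mmHg at s = 6, 8 and 10. With the two dips it is about −24, −27 and −31. An observed −27 therefore fits dips at s = 8, or no effect with s between 8 and 10. The combination with a known no-effect value is M + m (about zero), and it performs about as well as P.

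Direction is still blurred in P when an effect exists: with the two dips, 31–46% of children are represented by a rise; with heart rate +5 bpm, 29–36% are represented by a fall.

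**The case against.** The strongest case against is that little is lost. The row's minimum and maximum, if signed, show the group's single worst fall and worst rise. Appendix Table 4 is two-sided. By arithmetic, a 20 mmHg fall crosses the systolic limit of 90 from any value below 110, and a rise of 8/min crosses the respiratory limit of 20 from any value above 12. All values are listed, and AEs within 24 hours of an infusion are reviewed separately (SAP 5.8.2). No test or decision rests on the row. All of this stands, and it keeps the point minor. The cover is partial: fixed limits miss changes that stay inside them, the SAP does not say that the counts will separate low from high, and the minimum and maximum describe one child each. ECG heart rate has no markedly abnormal criterion, although pulse rate is flagged in both directions and the protocol says for ECG that "Shift and frequency tables of predefined change abnormal of select ECG parameter values will be generated".

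A reader might infer three stronger points, and none is supported.

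- **That a one-direction row is about twice as sensitive to brief changes.** That needs a no-effect mean which depends on an unknown SD and on the number of readings. The usable contrast gives no such gain.
- **That an unsigned row could not show direction.** The selected value is summarised beside Baseline, so the difference of the two means recovers the signed mean change. The natural reading is in any case that the word absolute governs which reading is selected.
- **That the SAP departs from its own laboratory standard.** SAP 5.8.4 does say "If a specific test can have both a significant low and high, then a shift table will be generated for each direction", but that governs categorical shift tables. The laboratory change summary is itself a single highest/lowest value.

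**Conclusion.** The point holds as a minor, cheap improvement to a display that serves the primary objective. For these four variables the plan mixes rises and falls in one mean and median and discards each child's opposite extreme, and SAP 6.1 leaves only the final observation as another change summary. That much follows from the wording and needs no assumption.

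The sizes rest on assumed SDs, independent readings and means that are stable over two years in growing children. On that footing the mean of a 20-child BP row wanders by about ±10 to ±17 mmHg with no effect, and the discarded extreme is about 55% of the kept one. What two rows add is a legible typical largest rise and typical largest fall. They do not make the safety analysis materially more sensitive, and the documents do not support a claim that a real signal would be missed in the report as a whole.

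**What to change.** In SAP 5.8.5 (systolic BP, diastolic BP, respiratory rate) and 5.8.6 (ECG heart rate), replace the largest-absolute-change value by two signed rows: each child's maximum change from Baseline and each child's minimum change from Baseline. Defining them as maximum and minimum, rather than as largest rise and largest fall, also covers a child who never rose or never fell. State that changes keep their sign.

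Cost: one sentence in each of two sections and one extra table row for each of four variables, with no new data.

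Downside to note in the table footnote: neither row has a fixed no-effect value, and both grow with the number of readings. At an assumed SD of 8 with no effect, the mean largest increase is about 24 with 384 readings and about 10 with the 6 scheduled post-baseline visits of an untreated child. The rows must not be read as a between-group comparison, which SAP 6.1 already rules out.
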